Attendees will then divide into small groups based on the identified priorities, develop recommendations for carrying out those priorities, and present plans to the larger group of attendees. Action plans may include a timeline for next steps or a list of other individuals and organizations to engage. The forum also may identify priorities for future research and intervention development.

Outcome Measure(s)

Primary outcome measures are COVID-19 testing and vaccination, including ever being tested, ever being vaccinated, being up to date on recommended doses, and number of doses received.

Analytical Plan

Aim 1:

In-depth interview and focus group data analysis. We will analyze the qualitative data using constant comparison, a systematic approach to developing grounded theory_{144,157} that is well-suited to uncovering participants' meanings and experiences. 144,157,158 It combines inductive coding with simultaneous comparison; initial observations are continually refined throughout data collection and analysis. 149,157,159 The goal is to identify themes, not to quantify participant experiences. 12,62,160,161 Analytical steps include:

- Interviewers will document post-interview and focus group impressions (e.g., content, process, and themes).
- Interviews and focus groups will be professionally transcribed and translated (if needed). Translation allows for simultaneous, collaborative analysis and iterative discussion of themes to yield more accurate findings.
- Interviewers will verify transcripts by reviewing and correcting discrepancies while listening to the recording.
- Transcripts will be managed using the NVivo (Chicago, IL) and examined to identify and code domains for theme development. 145,163 This will begin with analysts reading the same 3 transcripts and writing memos (written records of the analysis process linked to the specific transcript). These represent conceptual, theoretical, and operational notes to help compare domains within and across interviews and focus groups and inform the initial analytical coding scheme. 144
- The analysts will meet to develop a common coding system and data dictionary.
- All transcripts will be coded by at least 2 analysts (allowing for the addition of emerging codes).
- For data triangulation, analysts will develop, compare, then revise matrices that identify similarities and differences and explore emic and etic perspectives within and across participant categories (e.g., health providers v. Latinx-serving community-based organization representatives; health provider/organization representative interview v. Spanish-speaking Latinx community member focus group).160
- The CBPR partnership will review themes for validity (e.g., rigor, credibility, and trustworthiness).97,164-167

Aim 1 draws from a rich and thorough set of state-wide experiences that reflect millions of testing and vaccination encounters and the diverse perspectives of Spanish speakers and those who directly serve them across a wide range of settings. Thus, it will accomplish the most comprehensive qualitative assessment to date of SEBI of COVID-19 testing and vaccination among Spanish-speakers. Our results, in addition to informing Aim 2, will be important in their own right to inform other researchers and practitioners. Accordingly, results from Aim 1 will be shared as soon as available with RADx-UP CDCC and consortium.

Aim 2:

Hypotheses. We anticipate that participants in the intervention group, relative to their counterparts in the delayed-intervention group, will demonstrate increased COVID-19 testing and vaccination.

Quantitative data analysis plan. Data analysis will include **study group description** and **intervention impact evaluation**. *Study group description*. Frequencies and percentages for categorical variables and means, medians, standard deviations, and ranges for continuous variables will be tabulated to describe the sample. Reliability for measures will be estimated via internal consistency using coefficients alpha and omega. 178 Baseline intervention and delayed-intervention group comparisons will be performed. Correlation analyses will evaluate the associations between pairs of variables. Nonparametric statistics will be used when appropriate to evaluate significance of associations.

Evaluation of intervention impact. Data will be analyzed with an intent-to-treat approach.179 Randomization at the social network level will likely balance cluster-level baseline characteristics; however, as randomization may not precisely balance these, and there may be differences in social network member characteristics after network randomization, inverse probability weighting using propensity scores will be explored to balance baseline characteristics (both network and individual) between arms₁₈₀ using best practices.₁₈₁ Balance on propensity scores between intervention groups will be assessed using standardized differences.182 Propensity scores have been used in cluster RCTs.183 We will evaluate the intervention impact by comparing rates of past 6-month COVID-19 testing and vaccination completion (defined as complete dosage of approved vaccination: e.g., 2 Pfizer or Moderna doses or 1 Johnson & Johnson dose) between intervention and delayed-intervention group social network members at immediate post intervention (6 months after the intervention group *Navegantes* are trained), adjusting for baseline rates. This ANCOVA approach has the advantage of being unaffected by baseline differences; if baseline rates, by chance, were different, the intervention effect would be overestimated by looking at change scores and underestimated by a follow-up score analysis. The ANCOVA approach gives the same answer regardless of baseline imbalance. Additionally, the approach generally has greater statistical power to detect an intervention effect than the other methods. 184 Statistical analysis will be performed using generalized linear mixed modeling 185 for binary outcomes (sometimes termed randomeffects logistic regression). These models can assume a logit link for binary data (i.e., tested or vaccinated in past 6 months: yes/no) and allow for accounting for the within-group association of outcomes. If participants have repeated COVID-19 testing performed then an additional random effect for multiple testing will be considered, where appropriate. The generalized linear mixed model is an extension of general linear models that allows for non-independence of observations (e.g., within social networks).

The hypothesis that intervention and delayed-intervention groups differ in their prevalence, p, of COVID-19 testing or vaccination will be tested with the mixed-effects logistic model: Logit $(p_{ij}l) = \beta_0 + \beta_1 Y_{ijo} + \beta_2 INTVN + v_i$, where $p_{ij}l$ is the probability of testing or vaccination at immediate post-intervention for participant i in social network j, Y_{ij0} is 1 if participant i in social network j reports testing or vaccination at baseline and 0 otherwise, and, INTVN =1 for the intervention group and 0 for the delayed-intervention group. The random effect v_j is the random effect for participants in social network j. The variance component for this random effect addresses the within-social network correlation. Under this model, β_2

corresponds to the difference in prevalence of testing or vaccination at immediate post-intervention between the intervention and delayed-intervention groups on the logit scale. This random-effects logistic regression model will be fit using adaptive Gaussian quadrature in SAS PROC GLIMMIX.186

This regression approach will allow us to produce estimates of prevalence and prevalence change additionally *adjusting for individual and cluster-level covariates*, which will be compared to unadjusted estimates. Individual-level covariates may include age, country of origin, employment status, and education level. Because there are only a small number of clusters (social networks), the literature advises that the number of cluster-level covariates should be limited to one or two key variables. 187, 188 To assess the importance of covariates, we will use a backwards elimination model building approach, with primary consideration on assessment of confounding on the intervention-group difference. If confounding is present (defined to be greater than a 10% change in the regression estimate of the intervention-group effect), the confounder will be retained in the multivariable model. If many confounders are retained, alternative/sensitivity analyses will be conducted using propensity score weighting. All analyses will be 2-sided. 189 Note: While a better understanding of the relationships between members of social networks can be interesting, social network analysis is beyond the scope of this proposal based on our hypotheses and analysis plans.

Quantitative data collection/management. Assessment data will be collected by the study team in a safe and private location using audio-computer-assisted self-interview (ACASI) technology. We most recently used ACASI in our *weCare* intervention for English and Spanish data collection₉₋₁₄ and have worked out logistical details (e.g., data saving and backup) and ways to maintain participant interest. ACASI data collection overcomes challenges of literacy and will be conducted in Spanish. Saved ACASI files will be transferred using the Warehouse Manager to SAS data files for analysis and stored on a password protected secure server.

In-depth interview data analysis. Analysis of the data from in-depth interviews with *Navegantes* will mirror the qualitative data analysis processes described above in Aim 1.

Aim 3:

We will develop a final report of findings and practice, research, intervention, and policy priorities and recommendations to distribute to attendees, the RADx-UP CDCC and consortium, and others for whom the findings will be relevant (e.g., local and state-level health department leaders). We successfully used this approach previously to translate findings into action in a study of HIV disparities among sexual minority men. Subsequent actions led by forum attendees were (1) redirection of NC state prevention funds to develop safe spaces for facilitated group dialogue around intimacy and HIV risk; (2) a statewide conference to develop advocacy skills among community leaders; and (3) a new research partnership to explore the impact of immigration policy on healthcare use within Latinx communities.26,100

Human Subjects Protection

Subject Recruitment Methods

Aim 1:

In-depth interview and focus group participants for Aim 1 will be recruited through our partnership's broad networks of collaborators and community partners and by word-of-mouth.

Aim 2:

Protocol version: Template updated 9.24.14 Intervention participants for Aim 2 can be recruited as a *Navegante* or social network member of a *Navegante*. Potential *Navegantes* will be recruited by being invited to an individual interview in which we will explore eligibility and personal, performance, and situational characteristics relevant to serving as a *Navegante*. We will then select *Navegantes*. After enrolling, each *Navegante* will be provided a script and recruitment materials to present to their social network members, explaining the study and asking them to contact staff using the study's toll-free number to enroll.

Informed Consent

Verbal informed consent will be obtained from each focus group participant, and signed informed consent will be obtained from each Navegante and each social network member participant. The investigators or other study staff will obtain informed consent in community-based settings before collecting data from participants.

Interview participants will be provided with a brief description of the study to review before deciding to participate.

Confidentiality and Privacy

Confidentiality will be protected by collecting only information needed to assess study outcomes, minimizing to the fullest extent possible the collection of any information that could directly identify subjects, and maintaining all study information in a secure manner. To help ensure subject privacy and confidentiality, only a unique study identifier will appear on the data collection form. Any collected patient identifying information corresponding to the unique study identifier will be maintained on a linkage file, store separately from the data. The linkage file will be kept secure, with access limited to designated study personnel. Following data collection subject identifying information will be destroyed six years after closure of the study, consistent with data validation and study design, producing an anonymous analytical data set. Data access will be limited to study staff. Data and records will be kept locked and secured, with any computer data password protected. No reference to any individual participant will appear in reports, presentations, or publications that may arise from the study. A limited dataset will be sent to the CDCC via a secure web portal. Data will be stored by the CDCC on protected, secure computer systems. Anyone with permission to see these data will have to use a password and multi-factor authentication.

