Aim 2: Refine and test *NuestraSaludSegura* to determine its impact on COVID-19 testing and vaccination among Spanish-speaking Latinx persons using a group-randomized trial design.

Integrating our successes with peer navigation and mHealth strategies with other relevant COVID-19 studies and Aim 1 findings, we will refine and test the *NuestraSaludSegura* intervention. We will enroll 20 peer navigators, known as *Navegantes*, who represent 20 unique social networks, and 8 unique members from each social network for a total of n=160 social network members. After baseline data collection, we will randomize *Navegantes*, coupled with their social networks, into intervention and delayed-intervention groups (10 *Navegantes*; 80 social network members per group). We will train and support intervention-group *Navegantes* to increase COVID-19 testing and vaccination services within their social networks. We will evaluate the intervention by comparing changes in testing and vaccination from baseline to post-intervention follow-up between groups. *We hypothesize that intervention group will demonstrate increased COVID-19 testing and vaccination*.

Aim 3: Develop and disseminate practice, research, intervention, and policy priorities and recommendations to increase COVID-19 testing and vaccination among Spanish-speaking Latinx communities in the US. We will conduct an empowerment theory-based forum with Latinx community members and other community members and representatives from community-based organizations and universities to develop and disseminate priorities and recommendations based on study findings.

Methods and Measures

Design

Aim 1:

We will conduct **individual in-depth interviews** with two categories of participants from across NC: (1) Health providers (including administrators, clinicians, community health workers, and safety-net clinic staff), who have planned, managed, and/or conducted COVID-19 testing and/or vaccination activities for Spanish-speaking communities; and (2) Representatives from Latinx-serving community-based organizations. We also will conduct **focus groups** with Spanish-speaking Latinx community participants.

Aim 2:

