We will refine and test the *NuestraSaludSegura* intervention, integrating our previous successes with peer navigation and mHealth strategies with other relevant COVID-19 studies and Aim 1 findings. We will then recruit, enroll, and collect baseline data from 20 *Navegantes* (peer navigators) and their social network members (n=8 unique social network members per *Navegante*) from across NC. *Navegantes* (coupled with their social networks) will be randomly assigned to: intervention or delayed-intervention groups (10 *Navegantes*; 80 social network members per group). Intervention-group *Navegantes* will be trained and supported for 6 months of implementation in Years 1-2; delayed-intervention group *Navegantes* will be trained in Year 2. CBPR partners emphasized that a delayed-intervention comparison design is the most equitable, acceptable, and ethical.

Assessment of intervention efficacy. We will use a longitudinal group-randomized trial design with 2 arms (intervention and delayed-intervention) to evaluate the impact of the intervention. Quantitative outcome data will be collected from each *Navegante* and their 8 enrolled social network members at 2 time points: (1) baseline (*prior* to randomization and *Navegante* training) and (2) immediate post-intervention (6 months after the *Navegantes* in the intervention group are trained).

In-depth interviews. After post-intervention follow-up, we will conduct in-depth interviews with each *Navegante* in the intervention group (N=10) to explore and better understand their implementation of the intervention, their natural helping behaviors, and other lessons learned.

Aim 3:

The translation of findings into action is a CBPR hallmark,16,26,30,93-95,97,99,100,105,111,129,137,143,190-193 and we have developed an empowerment theory-based100,169,194,195 and highly collaborative process to do just that.95,100,166 We will organize and conduct a bilingual community forum to translate findings into practice, research, intervention, and policy priorities and recommendations.

Setting

The study will take place in community settings (e.g., community organizations) across NC.

Subjects selection criteria

• Inclusion Criteria

Aim 1:

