Based on our partnership's history training peer navigators,15-28 we currently have a *Navegante Training Manual*, which will guide the 4-session interactive training of the *Navegantes*, including sections on effective facilitation, how to prepare for training, session checklists, and all training activities and materials. This manual will require refinements related to COVID-19. We also will develop a *Navegante Resource Guide* that will provide details about COVID-19 testing and vaccination across NC (e.g., local providers and services and eligibility information) that *Navegantes* can refer to as they work with their social networks after training.

We will refine our *weCare* library of theory-based sample messages₁₀ that *Navegantes* can tailor and use to meet the specific needs of each social network member. We have much experience with mHealth message development to improve health outcomes._{9,10,12,14,29,99,135,173} A critical component of *NuestraSaludSegura* is the "connection" between the *Navegantes* and social network members. Growing evidence suggests that in-real-time, personalized, and bidirectional social support and problem solving provided by a peer using mHealth may be more successful in changing behaviors among populations facing many multilevel barriers to change than other technology-based approaches, such as software applications providing automated messages._{12,14,29,174-176} In our research to better understand the mechanisms underlying *weCare*, we discovered the importance of participants "knowing the person behind the messaging" and perceiving that this person cares about them.₁₂

Table 1. Activities of Navegantes in the NuestraSaludSegura intervention

Activities Raise awareness of the ongoing need for COVID-19 testing and vaccination Provide information and referrals De-mystify the process of seeking COVID-19 testing and vaccination Reframe and bolster norms and expectations

Share announcements and reminders

Troubleshoot and problem solve SEBI of COVID-19 testing and vaccination

Support communication with providers and staff

Support other prevention behaviors

Provide feedback to providers and staff

Examples

Navegantes increase consciousness among their social networks about the need for testing and vaccination to slow the spread of COVID-19, state and local rates of testing and vaccination and among Latinx populations, and the importance of taking action.

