Navegantes meet with providers and staff at COVID-19 testing and vaccination sites to provide feedback for multilevel changes to improve accessibility for Spanish-speaking Latinx communities.

Baseline and immediate post-intervention assessment. We will develop a Spanish-language assessment to collect data at baseline and immediate post-intervention (6 months post-baseline), based on Aim 1 findings, other relevant studies describing factors influencing COVID-19 testing and vaccination, our previous successes with peer navigation and mHealth strategies, and the theories underlying the intervention. **Table 2** outlines *draft* measurement priorities identified by our partnership while preparing this application. To ensure data harmonization, we will use the RADx-UP Common Data Elements and PhenX toolkit (https://www.phenxtoolkit.org/). The assessment, including final selection of measures,

Protocol version: Template updated 9.24.14 will be created using an *iterative* process by partners, including consultation with the RADx-UP CDCC and consortium

Table 2. Measurement priorities

Other variables

Outcome variables Primary: COVID-19 testing and vaccination including ever being tested, ever being vaccinated,

being up to date on recommended doses, and number of doses received

Demographic variables Age and date of birth; birthplace; ethnicity/race; language use; current living situation; zip code;

marital/partner status; family structure (e.g., children); educational attainment; current employment; financial status; immigration status; pregnancy status; insurance status

Symptoms COVID-19 symptoms and exposure to assess need for testing

Potentially mediating Awareness and knowledge about risk, testing, and prevention of COVID-19; intentions and variables readiness for COVID-19 testing and vaccination; perceived COVID-19 testing and vaccine a

readiness for COVID-19 testing and vaccination; perceived COVID-19 testing and vaccine access; knowledge of how to access testing and vaccination services; service use self-efficacy; perceived barriers to services; usual source of care; skills and self-efficacy to communicate effectively with providers; provider trust; history seeking and using prevention and care services; self-efficacy to overcome barriers; perceived provider discrimination; stigma related to COVID-19; social support; community attachment; perceived impact of positive test on job security; access to transportation

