Intervention acceptability; satisfaction with participation in intervention; interactions with

Navegante and social network members regarding COVID-19 testing and vaccination (to assess

contamination)

Navegante training and support. The Navegante training will be designed to increase knowledge and build skills as health advisors, opinion leaders, and community advocates in person and/or virtually and through mHealth. Navegantes will be trained to use a version of the "ask-advise-assist" model to provide guidance and help others and will be given a wallet-sized reminder card that outlines the steps, as we have done within peer navigation interventions in the past.19,70 Trained Navegantes will then carry out helping activities to increase COVID-19 testing and vaccination within their social networks for 6 months. During this time, Navegantes will be supported and meet with study staff as a group (monthly) and individually (as needed) for social support, intervention planning, experience sharing, and problem solving in person, virtually, by phone, and/or by social media. As part of the process evaluation, they will submit monthly Activity Logs (described below) to document their work with members of their social networks.(e.g., 20,50)

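### The single follow-up visit has two different clocks: 6 months after baseline in one section, 6 months after intervention-group training in two others

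*Combined protocol and SAP*

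**What the plan says.** The trial has two assessments, baseline and one follow-up. The timing of the follow-up is stated three times.

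- Design, Aim 2 (assessment of intervention efficacy): "immediate post-intervention (6 months after the" intervention-group *Navegantes* are trained.
- Analytical Plan, Aim 2 (evaluation of intervention impact): the arms are compared "at immediate post intervention (6 months after the intervention group" *Navegantes* are trained.
- Interventions and Interactions, Aim 2 (baseline and immediate post-intervention assessment): the assessment is to "collect data at baseline and immediate post-intervention (6 months post-baseline").

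The order of events is also stated. Objectives, Aim 2: "After baseline data collection, we will randomize" the *Navegantes* with their networks. Design, Aim 2, likewise puts baseline ahead of both randomization and training. There is a training manual, "which will guide the 4-session interactive training of the" *Navegantes*. Once trained, they "carry out helping activities to increase COVID-19 testing and vaccination within their social networks for 6 months".

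**The concern.** Only one follow-up exists, so the three statements must describe the same visit. Two are anchored to training and one to baseline. Because training comes after baseline, the baseline-anchored visit would take place while the intervention is still running, although it is called post-intervention.

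Two things are at stake if the visit is scheduled from baseline. First, the last part of the implementation period would go unmeasured. Second, the Analytical Plan's comparison looks back over a fixed period ("comparing rates of past 6-month COVID-19 testing and vaccination completion"). That window would then include time before training, when the intervention cannot yet have separated the arms, and this pulls the comparison toward no effect. The measures under Outcome Measure(s) (ever tested, ever vaccinated, up to date, number of doses) have no 6-month window, so for them only the shorter exposure matters.

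**Working it through.** **Timeline.** Let baseline be month 0 and let g be the months from baseline to completion of training.

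- Stated order: baseline, randomization, four-session training, 6 months of activity. Hence g > 0.
- End of intervention: month g + 6.
- Visit under Design and the Analytical Plan: month g + 6, the end of the intervention.
- Visit under the assessment paragraph: month 6, which is g months before the end.

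The two dates agree only if g = 0, which the stated order rules out. No section gives g, the calendar length of the training, or a visit window that would absorb the difference.

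**What follows from the 6-month period alone.** At a baseline-anchored visit, the share of implementation delivered is (6 − g)/6, and the share of the 6-month look-back that precedes completed training is g/6.

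**Illustration with assumed rates.** The documents give no event rates. Assume constant rates that produce 30% (delayed) and 50% (intervention) over 6 months, a 20-point difference.

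- Past-6-month outcome: intervention rate = 1 − 0.7^(g/6) × 0.5^((6−g)/6); subtract 0.30. For g = 1: 1 − 0.942 × 0.561 = 0.471, so the difference is 17.1 points.
- Ever tested or vaccinated: ratio of the between-arm difference at 6 − g months after training to that at 6 months = [0.7^((6−g)/6) − 0.5^((6−g)/6)] / 0.2. For g = 1: (0.743 − 0.561)/0.2 = 0.908. The ratio does not depend on baseline prevalence.

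| g (months, assumed) | End of intervention (month) | Delivered by month 6 | Look-back before training ends | Past-6-month difference (points) | Change from 20 points | Change, ever measures |
|---|---|---|---|---|---|---|
| 0.25 | 6.25 | 96% | 4% | 19.3 | −4% | −2% |
| 0.5 | 6.5 | 92% | 8% | 18.6 | −7% | −4% |
| 1 | 7 | 83% | 17% | 17.1 | −14% | −9% |
| 2 | 8 | 67% | 33% | 14.1 | −30% | −21% |
| 3 | 9 | 50% | 50% | 10.8 | −46% | −35% |

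**Sensitivity to when the effect accrues.** Keep the 30% and 50% six-month totals.

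- All excess in the first 3 months after training: the past-6-month difference stays at 20.0 points for g up to 3. The ever difference, among those without the event at training, is (2/7) × 0.7^(t/6) at t ≥ 3 months after training: 23.9 points at t = 3 against 20.0 at t = 6. An earlier visit then shows a larger difference.
- All excess in the last 3 months: at g = 1, two thirds of the excess has accrued, so the intervention rate is 1 − 0.7 × (0.5/0.7)^(2/3) = 0.441 and the past-6-month difference is 14.1 points.

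The ever formula describes a one-time yes/no event. It says nothing about being up to date or the number of doses.

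**The case against.** The intended rule can be read from the document. The Design section formally lists the two time points, and the Analytical Plan repeats the training anchor for the primary comparison. The conflicting paragraph is mainly about developing the questionnaire, and it too calls the visit post-intervention; only its parenthesis strays. Harm requires staff to follow that parenthesis against its own label and against two other sections. The gap, the rates and the accrual pattern used above are all assumed. Gaps of 2 or 3 months have no support in the text, and a loss on the ever measures is not guaranteed if the effect comes early.

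Most of this stands, and it limits the size of the problem. The chosen follow-up time is not in question; this is an inconsistency in how it is written down. The objection does not remove the contradiction. The paragraph is headed as the description of the assessment, so it is a natural place to look for visit timing. Baseline is also a date that every participant in both arms has, whereas the delayed group has no early training date of its own. Scheduling from it is plausible.

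**Conclusion.** The concern holds: the timing in the assessment paragraph is wrong as written. It contradicts two other sections and cannot describe a visit after a 6-month intervention that starts only once training is complete. Confidence in the textual conflict is high.

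The size of any bias is unknown because the gap is not stated. The documents support only that the gap exceeds zero and that each month of it affects one sixth of the implementation period and of the look-back. The point differences rest on assumed rates and accrual patterns and show scale only. The consequence is conditional on visits being scheduled from baseline; if the training anchor already governs, the data are unaffected. The correction should be made, since this is the trial's only outcome visit, but the point does not undermine the design.

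**What to change.** In the assessment paragraph under Interventions and Interactions, Aim 2, replace the baseline anchor with the one already used in Design and the Analytical Plan: 6 months after the intervention-group *Navegantes* are trained. State there that both arms are assessed on the same calendar timing; the other two sections imply this, so it only makes it explicit.

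The cost is a one-phrase edit. If the training anchor already governs scheduling, no visit moves. If visits had been scheduled from baseline, follow-up moves later by the length of the gap, and the sponsor should check how the new date sits against the delayed group's training in Year 2.
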